2.0 Objectives*

2.1 Describe the purpose, **specific aims**, or objectives.

Purpose: The purpose of this research is to develop a midlife **B**lack women's **Stress**-reduction **WELL**ness intervention, **B-SWELL**, to promote healthy lifestyle behaviors based on the stressors and themes identified in the PI's preliminary research and consistent with the American Heart Association's *Life Simple 7 Success Plan (LS7) behaviors*.

Aim 1: Develop the B-SWELL intervention for midlife Black women through the innovative leveraging of CBPR methodology and LS7 modifiable healthy lifestyle behaviors.

- a) To develop components of the B-SWELL intervention prototype for midlife Black women.
- b) Obtain ratings of the new components of the B-SWELL from an expert panel consisting of four midlife Black women laypersons, three researchers and three integrative health care specialists for degree of accuracy, relevance, and feasibility to inform further refinements.

Aim 2: Determine the feasibility of the B-SWELL intervention with a trial of 50 midlife Black women randomized to the B-SWELL intervention (25) or to a wellness education (WE) control group (25):

- a) Obtain recruitment, retention, treatment fidelity ratings, and satisfaction ratings for the intervention procedures for both groups, including technology;
- b) Compare mediator measures (stress, self-efficacy) for participants in the B-SWELL intervention group with those in the WE group at 8 and 12 weeks.
- c) Compare outcome measures (LS7 summary scores, unhealthy days, general health, depressive symptoms) for participants in the B-SWELL intervention group with those in the WE attention control group at 8 and 12 weeks.
- 2.2 State the hypotheses to be tested.

Our hypothesis proposes that B-SWELL (intervention) participants will show improved self-efficacy in managing life stress and adopting the LS7 behaviors, compared to an attention control group (WE group) receiving traditional wellness education.

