Interventions and Treatment Fidelity Methods: The B-SWELL intervention will follow procedures such as those proposed in Figure 1 and will be refined prior to trial based on feedback from the community collaborators and expert ratings (Aim1). Participants will be randomized to either the B-SWELL or WE groups. Both groups will be introduced to the LS7 materials. The B-SWELL will receive additional instruction about stress. B-SWELL and WE group sessions will occur on different dates and times and, participants will be asked not to share experiences with women outside of their assigned group. Participants will also be asked to secure private location when attending the virtual sessions to ensure privacy and confidentiality. Treatment fidelity of both groups will be monitored using Borrelli's Treatment Fidelity Checklist (Design, Training, Delivery, Receipt, Enactment). Facilitators of the intervention and control groups will be trained prior to the start of the trials.. Zoom meetings will be audio taped for quality assurance.

Data Collection Procedures: Aim 2. Data collection will occur at baseline, 8 weeks, and 12 weeks. Baseline data will be collected from B-SWELL and WE participants using telephone interviews conducted by trained, blinded research assistants. Data collection at 8 and 12 weeks may be collected via phone interview or through a REDCap link on the B-SWELL study tablets provided to B-SWELL and WE participant. Completion of the surveys (interview or via REDCap link) is expected to last 30-45 minutes for each timepoint. Instruments are listed in Table 5. 3.4.d.

Randomization Procedures: Following baseline data collection, participants will be randomized to either the B-SWELL or WE group using 1:1 block randomization to promote equal group sizes. The randomization allocation sequence will be blinded to data collectors to avoid bias during follow-up data collection telephone interviews. Following randomization, the PI or research assistant will notify the participant of their group assignment and upcoming group meetings. Treatment fidelity will be monitored using the Borrelli's Treatment Fidelity Checklist (Design, Training, Delivery, Receipt, Enactment).

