Tablets will be programmed with content and links relevant to the B-SWELL study and appropriate restrictions. Programming will be conducted by the B-SWELL research team under guidance of UC CATER staff. All study materials, including tablets, will be handled in accordance with UC COVID-19 protocols (i.e. gloves and masks).

• All drugs and devices used in the research and the purpose of their use, and their regulatory approval status.

N/A

• The source records that will be used to collect data about subjects. (Attach all surveys, scripts, and data collection forms.)

All study data and tracking will be entered into an electronic data system, REDCap (www.REDCap.org), a secure research electronic data management system with validated data entry, audit trails for tracking data manipulation, and export procedures. It is HIPAA complaint satisfying all local, state, and federal regulation for the capture and storage of private health information for research purposes.

Zoom accounts have been purchased by the UC CON. Zoom accounts will be supported by the UC CON CATER technology experts. Zoom links have been determined to be secure and appropriate for research by the UC depart of research. Members of the B-SWELL research team will be trained in the use and management of online Zoom group sessions, privacy, and technical issues.

The surveys used to collect data are included in the chart below and attached.

Construct	Survey Tool	Time	Baseline	8wks	12wks
Moderators	Demographic data: income, marital status, children, education, health problems, and community of residence (among others).	5	Х		
Mediator	Cohen's Perceived Stress Scale (PSS-10): measures perception of general stress. Items are rated on a scale of $0-4$ (Max score =40). ^{66,67} Higher stress levels correspond with higher scores.	5	X	Х	X
Mediator	General Self-Efficacy Scale (GSE): 10-item psychometric scale that assesses optimistic self-beliefs to cope with life demands ^{.68}	5	Х	Х	Х
Primary Outcome	AHA Life's Simple 7 (LS7): developed to promote cardiovascular health in accordance with the organization's 2020 Impact Goals. ⁶⁹ Risk behaviors scored 0 to 2. Higher scores indicate trend towards optimal health behaviors and lower risk for CVD.	5	X	X	X
Secondary Outcome	Number of Unhealthy Days (UD): Number of days in past month participant felt physical/mental health was not good. ⁷⁰	2	Х	Х	Х

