17.0 Data Management* and Confidentiality

17.1 Describe the data analysis plan, including any statistical procedures or power analysis.

In Aim 1 and Aim 2a, numerical measures will be summarized using descriptive statistics (i.e., means, standard deviations, and frequencies) regarding expert ratings of degrees of accuracy, relevance and feasibility of new components of the B-SWELL program (Aim 1), and recruitment, retention, treatment fidelity ratings, and satisfaction ratings (Aim 2a). For Aims 2b and 2c, numerical dependent variables (stress, self-efficacy, LS7 scores, unhealthy days, perceived general health, depressive symptoms) will be inspected of empirical distributions to ensure they meet conditions for parametric statistical models. Variable transformation will be used otherwise. All statistical tests will be performed using SPSS Version 25. Parameter estimates with P-values less than .05 will be considered statistically significant. Assumptions related to each statistical test used will be checked using residual plots, qq-plots, and tests for homogeneity of variance/ covariance. In Aim 2b, continuous mediators (stress, self-efficacy) will be compared between groups (B-SWELL vs WE) using t-tests at each visit (baseline, 8 weeks, 12 weeks).

In Aim 2c, using mixed effect models, primary (i.e., LS7 summary scores) and secondary outcome measures (i.e., unhealthy days, perceived general health, depressive symptoms) will be assessed for their associations with time (baseline, 8 weeks, 12 weeks), group (B-SWELL vs. WE), and interaction. In particular, each of the outcome measures will be treated as the dependent variable, and the time effect, group effect, and the interaction will be treated as independent variables or fixed effects of interest in the mixed effect model. Random effects will be used to account for within person correlation due to repeated measurements. Other covariates, such as demographics and attendance rate, will be controlled for by including them in the model and checking for their interaction with the intervention. Post hoc analysis of group means will be compared cross-sectionally, as well as longitudinally between time points (such as week 8 or 12 vs. baseline). Considering the limited sample size for this pilot-type of study, statistical tests will not be adjusted for multiple comparisons in post hoc analyses. Significant findings will be considered preliminary in nature and inspire future research.

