Power. Statistical power is analyzed based upon assumptions that we have N=50 total or N=25/group complete all four data collection time points with complete observations. Should there be any concern of dropout from the study, we will over sample participants at baseline to offset the predicted dropout rate and ensure the proposed sample size in the final visit. The statistical tests are two sided with a targeted significance level of 0.05. In Aim2b and Aim2c post hoc analyses when we compare means using a two group t-test with equal variances assumption, we will reach 85% power to detect an effect size (i.e. difference of means/standard deviation of the difference) of 0.87.73 In Aim2c when we compare means using a paired t-test between visits in a group, we will reach the 85% power to detect an effect size of 0.63.73 If possible, and plausible, missing data could be included into analysis after multiple imputation, thus increasing the sample size and statistical power to detect differences. The main emphasis will be on exploring data trends to inform future work, rather than

significance, since this is a feasibility study. Significance will be emphasized when testing efficacy of the B-SWELL intervention compared to the WE attention control group in a future, well-powered RCT.

17.2 Describe the steps that will be taken to secure the data during storage, use, and transmission.

All study data and tracking will be entered into an electronic data system, REDCap (www.REDCap.org), a secure research electronic data management system with validated data entry, audit trails for tracking data manipulation, and export procedures. It is HIPAA complaint satisfying all local, state, and federal regulation for the capture and storage of private health information for research purposes. The PI is familiar with RedCap through prior research projects. The PI is committed to compliance with HIPAA, data safety procedures, NIH recommendations, and CITI trainings. All research personnel will be trained in the use of secure data and RedCap prior to their participation in the study and any communication with participants.

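### The Aim 2b t-tests on stress and self-efficacy ignore the pre-randomisation baseline scores and so lose precision

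*Combined protocol and SAP*

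**What the plan says.** Section 17.1 sets the Aim 2b analysis: "continuous mediators (stress, self-efficacy) will be compared between groups (B-SWELL vs WE) using t-tests at each visit (baseline, 8 weeks, 12 weeks"). No covariate or change score is mentioned. The power paragraph of the same section assumes the same test: "In Aim2b and Aim2c post hoc analyses when we compare means using a two group t-test with equal variances assumption". It gives 85% power for an effect size of 0.87 with 25 completers per group.

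The Aim 2c outcomes are treated differently. They are analysed "using mixed effect models, primary (i.e., LS7 summary scores) and secondary outcome measures (i.e., unhealthy days, perceived general health, depressive symptoms"), with baseline as one of the time points. Stress and self-efficacy are not on that list, and the sentence on covariates belongs to the Aim 2c paragraph. Aim 2c also has a secondary step: "Post hoc analysis of group means will be compared cross-sectionally". That step is powered as the same two-group t-test.

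The baseline scores will exist. The survey table in section 6.3 schedules the stress scale and the "General Self-Efficacy Scale (GSE): 10-item psychometric scale" at baseline, 8 weeks and 12 weeks. Section 6.2.2 fixes the order: "Following baseline data collection, participants will be randomized to either the B-SWELL or WE group". The section 2.2 hypothesis is that "B-SWELL (intervention) participants will show improved self-efficacy in managing life stress and adopting the LS7 behaviors".

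**The concern.** A woman's baseline stress or self-efficacy score usually predicts her later score. A t-test on follow-up scores alone leaves that predictable variation in the error term. Any chance difference between the arms at baseline also carries into the follow-up difference, in proportion to r. The planned baseline t-test does not help, because testing for an imbalance does not correct it.

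Section 17.1 also states that "The main emphasis will be on exploring data trends to inform future work". If the product of this pilot is a set of estimates for planning the next trial, the width of the interval around each between-group difference matters more than its p-value. The plan gives the less efficient analysis to a variable named in its own hypothesis, although the data for a better one are already being collected.

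**Working it through.** **Inputs from the documents.** 25 completers per arm, two-sided 5% level, 85% power, effect size 0.87, two-group t-test with equal variances (section 17.1); 1:1 allocation after baseline collection (section 6.2.2).

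**Assumed input.** The correlation r between baseline and follow-up score is not given. I use 0.3, 0.5, 0.6 and 0.7. Effects are in units of the follow-up SD, with equal SDs at baseline and follow-up and independent participants.

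**Step 1: reproduce the plan's figure.** With 48 degrees of freedom the noncentrality is 0.87 × √(25/2) = 3.08, and noncentral-t power is 85.4%. The effect detectable at exactly 85% is 0.865 SD. The stated 0.87 is correct for the planned test.

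**Step 2: other properties of the planned t-test.**
- Standard error: √(2/25) = 0.283 SD.
- Expected 95% half-width: 2.011 × 0.283 = 0.569 SD.
- Power at a true difference of 0.6 SD: 54.7%.

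**Step 3: adjust for baseline.** ANCOVA multiplies the variance of the difference by (1 − r²). Estimating the slope costs a factor of (1 + 1/46) on average and one degree of freedom, leaving 47. The variance multiplier is therefore (1 − r²)(1 + 1/46). For r = 0.5 it is 0.75 × 1.0217 = 0.766, and the half-width is 2.012 × 0.283 × √0.766 = 0.498 SD.

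| | t-test | r = 0.3 | r = 0.5 | r = 0.6 | r = 0.7 |
|---|---|---|---|---|---|
| Variance multiplier | 1 | 0.930 | 0.766 | 0.654 | 0.521 |
| Detectable effect at 85% power (SD) | 0.865 | 0.834 | 0.758 | 0.700 | 0.625 |
| Power at 0.6 SD | 55% | 58% | 66% | 73% | 82% |
| Expected 95% half-width (SD) | 0.569 | 0.549 | 0.498 | 0.460 | 0.411 |
| Women per arm for a t-test with the same detectable effect | 25 | 26.8 | 32.3 | 37.7 | 47.0 |

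Simulation with 40,000 trials per value of r gave the same powers at 0.6 SD and a type I error of 0.049 to 0.052 for both methods. Validity is not at issue.

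**Step 4: when adjustment pays.** The multiplier falls below 1 when r² exceeds 1/47, that is, r above about 0.15. At r = 0 the variance cost is 1/46, about 2%.

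**Step 5: chance imbalance.** A one-standard-error baseline gap is 0.283 SD. The unadjusted follow-up difference then moves by r × 0.283 = 0.08, 0.14, 0.17 and 0.20 SD for the four values of r.

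**Step 6: change scores as an alternative.** Their variance multiplier is 2(1 − r): 1.4 at r = 0.3, 1.0 at r = 0.5 and 0.6 at r = 0.7. The detectable effects are 1.02, 0.87 and 0.67 SD. A change score is worse than the planned t-test when r is below 0.5, and worse than ANCOVA at all three of these values.

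**The case against.** The strongest reply is that nothing here is an error. The t-test is valid, its power is stated correctly, and the study is a development and feasibility project in which stress and self-efficacy are mediators. The survey table's primary outcome, the LS7 score, already has a mixed model. No decision is tied to the Aim 2b tests. All of that is true, and it limits how serious the point is. It does not remove it, because a study meant to yield estimates gains most from narrower intervals, and self-efficacy is in the stated hypothesis.

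The gain also depends on an r that the documents do not supply. This stands: at r = 0.3 the benefit is about two women per arm. The possible loss, however, is trivial.

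Both arms meet in group sessions, and baseline adjustment cannot remove variation between session groups. The documents give neither the number of groups nor an intraclass correlation. As an illustration, take two groups of 12.5 per arm and an intraclass correlation of 0.05. The design effect is 1 + 11.5 × 0.05 = 1.575. The standard error ratio from adjustment, before the slope cost, becomes √((1.575 − r²)/1.575): 0.92 at r = 0.5 instead of 0.87, and 0.97 at r = 0.3 instead of 0.95. The gain shrinks but remains. Independence is also the assumption behind the plan's own power figure.

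The imbalance figure in step 5 is not a second harm. It is the same loss of precision, seen in one realised trial.

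Section 23.2 mentions randomisation before baseline collection. That sentence only lists steps completed before an information sheet is mailed. The randomisation procedure in section 6.2.2 states the order explicitly, and I rely on it.

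Finally, Aim 2c already has a model that includes baseline. Its post hoc cross-sectional contrasts, however, are powered as the same unadjusted t-test, so the same remedy applies to them.

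**Conclusion.** The concern holds as a matter of efficiency, not of bias or error rate. For r between 0.3 and 0.7, the unadjusted comparison has a detectable effect of 0.87 SD where 0.83 to 0.62 SD is attainable, and an expected half-width of 0.57 SD where 0.55 to 0.41 SD is attainable. These figures assume 25 completers per arm, equal SDs at baseline and follow-up, a linear relation between baseline and follow-up score, and independent participants. The gain is slight at r = 0.3, material from about r = 0.5, and reduced if outcomes cluster by session group. The change should be made because it costs almost nothing, but the trial would not be invalid without it.

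**What to change.** In section 17.1, replace the Aim 2b t-tests at 8 and 12 weeks with one of these:

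- ANCOVA at each visit, with group and the baseline score of the same scale; or
- one repeated-measures model of the 8- and 12-week scores with group, visit, group by visit, baseline score and baseline by visit, using an unstructured 2 × 2 covariance or a random intercept.

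Report the adjusted between-group difference with its 95% confidence interval at each visit. Do not substitute a plain change score. Use the same baseline-adjusted contrast for the post hoc cross-sectional group comparisons in Aim 2c. Drop the baseline significance test and describe the baseline scores by arm.

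The cost is a wording change, one degree of freedom per ANCOVA or two in the joint model. No new data are required, and SPSS, the planned software, fits either model. The stated power can remain as the unadjusted figure, with a note that adjustment is expected to improve on it unless r is very low.

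### Aim 2c models the pre-randomisation baseline as an outcome visit and does not say which term tests the intervention; a baseline-adjusted contrast at weeks 8 and 12 would be clearer and more precise at no cost.

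*Combined protocol and SAP*

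**What the plan says.** - **Aim (section 2.1, Aim 2c).** Outcomes in the B-SWELL group are to be compared "with those in the WE attention control group at 8 and 12 weeks".
- **Timing (section 6.2.2, Randomization Procedures).** "Following baseline data collection, participants will be randomized to either the B-SWELL or WE group using 1:1 block randomization".
- **Model (section 17.1, Aim 2c).** The LS7 summary score and the secondary outcomes "will be assessed for their associations with time (baseline, 8 weeks, 12 weeks), group (B-SWELL vs. WE), and interaction". Then: "the time effect, group effect, and the interaction will be treated as independent variables or fixed effects of interest in the mixed effect model". Also: "Random effects will be used to account for within person correlation due to repeated measurements".
- **Covariates (section 17.1, Aim 2c).** Demographics and attendance rate are given as examples. The baseline value of the outcome is not mentioned, which is consistent with baseline sitting in the dependent variable.
- **Further comparisons (section 17.1, Aim 2c).** Post hoc comparisons of group means are planned cross-sectionally and between time points, with week 8 or 12 against baseline as the example.
- **Baseline testing (section 17.1, Aim 2b).** The two mediators, stress and self-efficacy, are compared between arms "using t-tests at each visit (baseline, 8 weeks, 12 weeks").
- **Power (section 17.1, Power).** With 25 per group and two-sided 0.05, the plan claims 85% power at an effect size of 0.87 for the two-group t-test. It attaches this to Aim 2b and the Aim 2c post hoc comparisons, not to the group term of the mixed model.

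**The concern.** Because baseline precedes allocation, the true arm difference there is zero. A model that treats baseline as an ordinary outcome visit and then lists group, time and their interaction side by side leaves open which result answers Aim 2c. The group term is the one a reader would most naturally take as the effect of B-SWELL, yet its meaning depends on a coding choice that the plan does not make:

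- averaged over visits, it mixes in a visit at which there can be no effect;
- with baseline as the reference level, it is the chance baseline difference;
- with week 12 as the reference level, it is the week-12 difference.

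A pilot that is meant to support a larger trial should not pass forward an effect size whose definition is this loose. In addition, the baseline measurement, already collected on everyone, is not used in the way that gives the most precise follow-up contrast.

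**Working it through.** **Inputs.** From the plan: three visits, 25 per arm with complete data, two-sided 0.05, effect size 0.87. Assumed, because the documents do not give them: 0.87 is in units of the outcome SD and is equal at weeks 8 and 12; SD is equal across visits; the within-person correlation rho is 0.3, 0.5 or 0.7 between any two visits (the structure a random intercept implies). Power is from the noncentral t with 48 df.

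**Step 1: the plan's own figure.** Two-group t-test, 25 per arm, 0.87 SD: 85.4%. The stated 85% reproduces.

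**Step 2: what the visit-averaged group effect estimates.** With balanced visits it is the mean of the three arm differences, (0 + d8 + d12)/3. With d8 = d12 = 0.87 this is 1.74/3 = 0.58. Relative to the mean follow-up effect (d8 + d12)/2 the ratio is 2/3 whatever the pattern over time. Relative to one visit alone it varies: if the week-12 effect is half the week-8 effect (0.87 and 0.435), the averaged effect is 1.305/3 = 0.435, half of the week-8 effect and equal to the week-12 effect.

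**Step 3: power of each candidate at 0.87 SD.** Standardised effect = effect / sqrt(variance factor).

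| Contrast | Effect | Variance factor | rho 0.3 | rho 0.5 | rho 0.7 |
|---|---|---|---|---|---|
| Group effect averaged over three visits | 0.58 | (1 + 2 rho)/3 | 79% | 69% | 61% |
| Week 8, cross-sectional | 0.87 | 1 | 85% | 85% | 85% |
| Week 8, change from baseline between arms (interaction contrast) | 0.87 | 2(1 - rho) | 72% | 85% | 97% |
| Week 8, baseline-adjusted | 0.87 | 1 - rho² | 88% | 94% | 99% |

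Worked at rho 0.5: averaged group effect 0.58/sqrt(0.667) = 0.710, power 69%; change 0.87/sqrt(1) = 0.87, power 85%; baseline-adjusted 0.87/sqrt(0.75) = 1.005, power 94%. The one degree of freedom spent on a covariate is ignored.

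**Step 4: gain over the change contrast.** Variance ratio = (1 - rho²)/(2(1 - rho)) = (1 + rho)/2, that is 0.65, 0.75 and 0.85 at rho 0.3, 0.5 and 0.7.

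**Step 5: dependence on coding.** A simulation of 400 trials with a random-intercept model (rho 0.5, true 0.87 at both follow-up visits) gave a mean averaged group effect of 0.57 with power 67%. The group coefficient averaged -0.02 with baseline as reference and 0.85 with week 12 as reference. One model, with the same data, therefore gives three different targets for the group effect.

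**Step 6: chance baseline imbalance.** The standard error of the baseline difference is sqrt(2/25) = 0.28 SD. The expected shift in the averaged group effect per SD of observed baseline difference is (1 + 2 rho)/3, so an imbalance of one standard error moves it by 0.15, 0.19 and 0.23 SD at rho 0.3, 0.5 and 0.7.

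**Step 7: baseline tests.** Aim 2b plans two. If they were independent, the chance of at least one false imbalance would be 1 - 0.95² = 9.8%.

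**The case against.** The strongest reply is that the plan already contains adequate estimates. The interaction is among the effects of interest, and the post hoc comparisons by visit can supply the week-8 and week-12 differences that Aim 2c asks for. The stated power is attached to those comparisons. Under randomisation, both the cross-sectional differences and the interaction contrasts are unbiased, and at rho 0.7 the week-8 change contrast has 97% power. This stands: a suitable estimate is available, and the remaining gain is one of precision and of naming the target.

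Three stronger readings are tempting, and the documents do not support them.

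- **That the Aim 2c effect is diluted by a third.** This holds only if the group effect is the visit-averaged one. The plan states no coding, and reference coding gives a different quantity.
- **That baseline imbalance biases the result.** Its expectation is zero under randomisation. It adds noise, and error conditional on the imbalance observed, but no systematic bias. The shortfall of the averaged effect comes from including a visit with no effect.
- **That six baseline tests give about a 26% chance of a false imbalance.** Section 17.1 explicitly plans baseline t-tests for two mediators. Six requires assuming that the Aim 2c cross-sectional comparisons also cover baseline, which the plan does not say.

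It is also fair to say that the plan calls significant findings preliminary and puts trends ahead of significance. That limits the consequence, but does not settle which trend is the intervention effect. The visit comparisons are labelled post hoc, and the longitudinal comparisons are powered as paired tests within a group, which are not comparisons between arms.

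**Conclusion.** The point holds as a gap in definition together with a free gain in precision. Section 17.1 lists three effects of interest without designating the one that tests B-SWELL. If the group effect is taken in its usual averaged sense, it targets two-thirds of the mean follow-up effect (0.58 for 0.87 SD), with 79/69/61% power at rho 0.3/0.5/0.7. The two-thirds ratio does not depend on rho; the power figures do, and they also assume equal effects at both follow-up visits and 25 complete cases per arm.

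Against the plan's own unbiased week-8 comparisons, baseline adjustment raises power from 85% (cross-sectional) or 72/85/97% (change) to about 88/94/99%. The documents do not support a claim that the Aim 2c analysis as a whole is biased or lacks a valid estimate of the arm difference. In an exploratory pilot the consequence is for how the result is read and for the effect size taken into the larger trial.

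**What to change.** In section 17.1, Aim 2c:

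1. Define the treatment effect for LS7 and each secondary outcome as the B-SWELL minus WE difference at week 8 and at week 12, reported with confidence intervals.
2. Estimate it from a mixed model in which the arms share one baseline mean: visit effects for all three visits, plus group-by-visit terms for weeks 8 and 12 only. Alternatively, model weeks 8 and 12 as outcomes with the baseline value as covariate.
3. State that the group main effect is not interpreted as the test of the intervention.

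Secondary, for Aim 2b: describe the baseline values of stress and self-efficacy by arm rather than testing them.

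The cost is a few sentences and a different coding of the same mixed model in the same software. No new data are needed, and the sample size and visit schedule do not change.
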